## 2. LIST OF ABBREVIATIONS

Term	Definition / description
AE	Adverse Event
AESI	Adverse Event of Special Interest
ALT	Alanine Aminotransferase
ANCOVA	Analysis of Covariance
AST	Aspartate Transaminase
ATC	Anatomical Therapeutic Chemical
AUC	Area under the curve
AUC 0-tz	Area under the concentration-time curve of the analyte in plasma over the time interval from 0 to the last quantifiable data point
████	████████████████████
CCT	Computerized Cognitive Training
████	██
CI	Confidence Interval
C max	Maximum measured concentration of the analyte in plasma
COVID-19	Coronavirus Disease 2019
C-SSRS	Columbia Suicidal Severity Rating Scale
DILI	Drug Induced Liver Injury
GlyT1	Glycine Transporter 1
gMean	Geometric Mean
IPD	Important Protocol Deviation
MATRICS	Measurement and Treatment Research to Improve Cognition in Schizophrenia
MCCB	MATRICS Consensus Cognitive Battery
MedDRA	Medical Dictionary for Drug Regulatory Activities
M.I.N.I.	Mini-International Neuropsychiatric Interview
MMRM	Mixed-effect Model Repeated Measures
PANSS	Positive and Negative Syndrome Scale
PoC	Proof-of-concept
████	██
PT	Preferred Term
REML	Restricted Maximum Likelihood

---

Term	Definition / description
REP	Residual Effect Period
SARS-CoV-2	Severe acute respiratory syndrome coronavirus 2
SCoRS	Schizophrenia Cognition Rating Scale
SOC	System Organ Class
	
WHO DD	World Health Organization Drug Dictionary

### **3. INTRODUCTION**

As per International Conference on Harmonisation (ICH) E9 [\(1\)](#), the purpose of this document is to provide a more technical and detailed elaboration of the principal features of the analysis described in the protocol, and to include detailed procedures for executing the statistical analysis of the primary and secondary variables and other data.

This Trial Statistical Analysis Plan (TSAP) assumes familiarity with the Clinical Trial Protocol (CTP), including Protocol Amendments. In particular, the TSAP is based on the planned analysis specification as written in CTP Section 7 “Statistical Methods and Determination of Sample Size”. Therefore, TSAP readers may consult the CTP for more background information on the study, e.g., on study objectives, study design and population, treatments, definition of measurements and variables, planning of sample size, randomization.

SAS® Version 9.4 will be used for all analyses [REDACTED] if not specified otherwise. [REDACTED]

## 5. ENDPOINTS(S)

The primary objective of this trial is to provide proof-of-concept (PoC) data to assess the effect on cognition of oral once daily administration of BI 425809 given for 12 weeks in patients with schizophrenia on stable antipsychotic treatment and adjunctive computerized cognitive training (CCT).

Other objectives of this trial are to explore endpoints to assess functioning and well-being of patients with schizophrenia, and to evaluate safety and pharmacokinetics of BI 425809.

Endpoints in this trial and their associated measurement time points are listed in Table 5: 1.

Table 5: 1 Endpoints and time points of measurement

Visit 1	Visit 2	Visit 3	Visit 4	Visit 5	Visit 6 (e)EoT	Follow-up
Screening	Baseline	Week 3	Week 6	Week 9	Week 12 (EOT) / eEOT	Week 16 / eEoT + 28 day
Day -28 to -1	Day 1	Day 22	Day 43	Day 63	Day 84	(e)EoT + 28
MCCB	MCCB		MCCB		MCCB	
PANSS	PANSS		PANSS		PANSS	
SCoRS*	SCoRS				SCoRS	
	████				████	
	██████				██████	
	██				██	
	██████				██████	
C-SSRS	C-SSRS	C-SSRS	C-SSRS	C-SSRS	C-SSRS	C-SSRS
CCT**	CCT**					
		██	████	████	████	

\*Screening SCoRS is added in Global Protocol Amendment 3 (version 4.0).

\*\*CCT usage and performance is recorded and assessed throughout the run-in/screening period and the on-treatment period.

### 5.1 PRIMARY ENDPOINT(S)

The primary endpoint is

- Change from baseline in MCCB neurocognitive composite T-score after 12 weeks of treatment

The primary endpoint will be used as defined in CTP Section 5.1.

#### MCCB

MCCB neurocognitive composite T-score is derived from the 6 domains: 1) Speed of Processing, 2) Verbal Learning, 3) Working Memory, 4) Reasoning and Problem Solving, 5) Visual Learning, and 6) Attention/Vigilance. A higher score indicates better cognitive function.

## **5.2 SECONDARY ENDPOINT(S)**

### **5.2.1 Key secondary endpoint(s)**

Not applicable. No key secondary endpoints in this trial.

### **5.2.2 Secondary endpoint(s)**

The secondary efficacy endpoints are:

- Change from baseline in MCCB overall composite T-score after 12 weeks of treatment
- Change from baseline in SCoRS total score after 12 weeks of treatment
- Change from baseline in PANSS total score after 12 weeks of treatment

The secondary safety endpoints is:

- Percentage of patients with (S)AEs

Unless otherwise specified, the secondary endpoints will be used as defined in CTP Section 5.

#### MCCB

MCCB overall composite T-score is derived from all 7 domains: 1) Speed of Processing, 2) Verbal Learning, 3) Working Memory, 4) Reasoning and Problem Solving, 5) Visual Learning, 6) Attention/Vigilance, and 7) Social Cognition.

#### SCoRS

SCoRS interviewer total score will be used for secondary endpoint analysis.

[figure not shown]
#### PANSS

[figure not shown]
PANSS has 30 items, each rated from 1 to 7 points. The PANSS total score will be calculated as the summation of the item scores, leading to a total score ranging from 30 to 210.

[figure not shown]
The PANSS total score is calculated only if the number of missing item scores is  $\leq 6$  (i.e.  $\leq 20\%$  of the 30 items). Otherwise, the total score will be left as missing. See [Section 6.6](#) for imputation and derivation rules.

## 6. GENERAL ANALYSIS DEFINITIONS

### 6.1 TREATMENT(S)

For basic study information on treatments to be administered, assignment of treatment groups, selection of doses, refer to CTP Section 4.

Table 6.1: 1 lists the two treatment arms in this study. Table 6.1: 2 defines the analysing treatment period for safety analysis. For this study, the residual effect period (REP) is defined as 11 days after the last dose of trial medication.

Table 6.1: 1 Treatment descriptions

Long Name	Short Name
Placebo + Computerized Cognitive Training	Placebo + CCT
BI 425809 10 mg + Computerized Cognitive Training	BI 10 mg + CCT

Table 6.1: 2 Analysing treatment periods (same for all treatment groups)

Analysing Treatment Period	Start Date	End Date (inclusive)
Screening	Date of informed consent	Date of the first treatment administration – 1 day
On-Treatment	Date of the first treatment administration	Date of the last treatment administration + REP
Follow-up	Date of the last treatment administration + REP + 1 day	Date of the last per protocol visit

Residual effect period (REP) is defined as 11 days after the last dose of study medication.

### 6.2 IMPORTANT PROTOCOL DEVIATIONS

Handling of iPDs in analysis is included in the DV domain specifications and stored within the TMF in EDMS.

Identification of iPD will be finalized at database lock (DBL). For iPDs identifiable only from unblinded data, rules are pre-specified in the DV domain specification.

### 6.3 SUBJECT SETS ANALYSED

The following patient analysis sets are defined:

- **Randomized Set (RS):** includes all patients who signed informed consent and were randomized to receive either BI 425809 + CCT or placebo + CCT. Patients will be analysed as randomized.

- **Treated Set (TS):** includes all patients in RS who were treated with at least one dose of the trial regimen (including both drug and CCT). TS will be used for safety analyses as well as demographics and baseline characteristics and treatment regimen exposure. Patients will be analysed under the actual trial regimen received at randomization.
- **Full Analysis Set (FAS):** includes all patients in TS who had non-missing baseline and at least one non-missing post-baseline on-treatment measurement of the primary efficacy endpoint. FAS will be used for efficacy analyses. Patients will be analysed as randomized.

Table 6.3: 1 Subject sets analysed

Class of endpoints	Subjects Sets Analysed				
	TS	FAS			
Primary endpoint		Primary analysis			
Secondary efficacy endpoints		Primary analysis			
Safety variables	X				
Demographic/baseline variables/exposure	X				

[Redacted text]

[Large redacted area]

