7.3 PLANNED ANALYSES

The following patient analysis sets are defined for this trial:

- Randomized Set (RS): includes all patients who signed informed consent and were randomized to receive either BI 425809 + CCT or placebo + CCT.
- Treated Set (TS): includes all patients in RS who were treated with at least one dose of the trial regimen (including both drug and CCT). Patients in TS are analyzed under the actual trial regimen received at randomization. The TS is used for safety analyses as well as demographics and baseline characteristics and treatment regimen exposure.
- Full Analysis Set (FAS): includes all patients in treated set who had non-missing baseline and at least one non-missing post-baseline on-treatment measurement on the primary efficacy endpoint. The FAS is used for efficacy analyses and patients will be analyzed as randomized.

- 

Data from patients who were screened but not randomised will be listed but not included in any inferential statistics.

The list of IPDs is described in the study TSAP.

Handling of randomised patients who received the wrong treatment will be specified in the TSAP.

Baseline

The baseline for MCCB neurocognitive composite score, and all other efficacy-related endpoints is defined as the measurement taken at randomization (Visit 2), and prior to the first administration of the study drug.

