## 6.7 BASELINE, TIME WINDOWS AND CALCULATED VISITS

In general, baseline value will be the measurement taken on the day of randomization (Visit 2), and prior to the first study medication administration. If this value is not available, the measurement at the screening visit (Visit 1) will be used, except for MCCB assessments.

Baseline for MCCB neurocognitive composite score and related endpoints is defined as the measurements taken at randomization (Visit 2), and prior to the first administration of the study medication.

Analysis visit will be used for by-visit summaries and analysis of efficacy endpoints. Study day windows for mapping to analysis visits are presented in Table 6.7: 1. Actual study day will be calculated starting with day of randomization as Day 1. If more than one assessment is mapped to the same post-baseline analysis visit, the closest assessment to the planned study day will be used. In case of a tie, the earlier assessment will be used.

Table 6.7: 1 Analysis visit windows

Analysis visit	Nominal Timepoint	Planned study day	Actual study day window	
			MCCB*, PANSS	Other efficacy assessments
2	Baseline	1	≤1	≤1
4	Week 6	43	2 – 60	
6/EoT	Week 12	85	≥61	≥2

\*MCCB assessments taken >12 days after the last study medication intake will not be included in the analysis.

Safety endpoints will be summarized based on nominal visits as reported in the CRFs. No re-labelling to analysis visits will be performed.

In subject data listings, all data at scheduled or unscheduled timepoints will be presented.

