### 7.5.2 (Other) Secondary endpoint(s)

#### 7.5.2.1 Primary analysis of the secondary endpoints

Primary analysis of the secondary endpoints will be conducted on FAS. Estimated least squares mean difference between the two treatment arms will be provided together with 95% confidence intervals. Statistical model and estimation method for each secondary endpoint are described below.

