#### SCoRS interviewer total score

The primary analysis of change from baseline in SCoRS interviewer total score after 12 weeks of treatment will be an ANCOVA based approach using the following model:

$$y_{ikm} = \tau_k + \beta X_i + \phi_m + e_i$$

$$e_i \sim N(0, \sigma^2)$$

where

- $y_{ikm}$  = response variable for subject  $i$  in age stratum  $m$  receiving treatment  $k$ ,  
 $\beta$  = coefficient of baseline effect,  
 $X_i$  = baseline value of subject  $i$ ,  
 $\tau_k$  = effect of treatment  $k$ ,  
 $\phi_m$  = effect of age stratum  $m$   
 $e_i$  = random error associated with subject  $i$ , independently distributed ,  
across subjects

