#### PANSS total score

The primary analysis of change from baseline in PANSS total score after 12 weeks of treatment will be a REML based approach using the following simplified MMRM from that in [Section 7.4.1](#):

$$y_{ijkm} = \tau_{jk} + \beta_j X_i + \phi_m + e_{ij}$$

where  $X_i$  = baseline score of subject  $i$ , while the other covariates and parameters are same as defined in Section 7.4.1.

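### SCoRS and PANSS are analysed on a set gated by MCCB, so a few valid ratings can be left out for no modelling reason; a low-severity, cheap improvement

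*SAP*

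**What the plan says.** SAP 6.3 admits a patient to the FAS if the record "includes all patients in TS who had non-missing baseline and at least one non-missing post-baseline on-treatment measurement of the primary efficacy endpoint". Protocol 7.3 has the same rule and adds: "The FAS is used for efficacy analyses and patients will be analyzed as randomized". SAP 5.1 names the primary endpoint as change in the MCCB neurocognitive composite T-score. Under SAP 6.7 the MCCB baseline must come from Visit 2.

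For the secondary endpoints, SAP 7.5.2.1 states: "Primary analysis of the secondary endpoints will be conducted on FAS". SAP Table 6.3: 1 and Protocol 7.3.2 agree. The two models concerned are:

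- SCoRS: "The primary analysis of change from baseline in SCoRS interviewer total score after 12 weeks of treatment will be an ANCOVA based approach". Its terms are treatment, baseline SCoRS and age stratum.
- PANSS: "The primary analysis of change from baseline in PANSS total score after 12 weeks of treatment will be a REML based approach". Its terms are treatment by visit, baseline PANSS by visit and age stratum.

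After baseline, MCCB is scheduled only at Visit 4 and (e)EoT, PANSS at the same two visits, and SCoRS at (e)EoT only (Protocol 5.1). Protocol 10.5 lets SCoRS and PANSS be rated by phone when a patient cannot attend, but not MCCB. SAP 6.6 and 6.7 exclude MCCB taken more than 12 days after the last dose; the readable text has no such rule for the other scales.

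**The concern.** The gate does no work in the SCoRS and PANSS models, since neither conditions on MCCB. Its only effect there is to remove patients whose cognitive battery is missing, whatever else was measured. Protocol 10.5 makes such patients possible by allowing the two rating scales, but not the battery, at a phone visit.

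Two things are at stake, both minor. Some precision is lost on two secondary endpoints. A selection step after randomisation, on MCCB availability, is also added to models that do not need it. Protocol 7.5 relies on a missing-at-random argument for the MMRM. That argument is best served by using every observed value of the outcome being modelled.

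**Working it through.** **1. Set logic.** Applying the FAS rule to each pattern of usable MCCB:

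| Visit 2 | Visit 4 | (e)EoT | In FAS? |
|---|---|---|---|
| yes | yes | yes | yes |
| yes | yes | no | yes |
| yes | no | yes | yes |
| yes | no | no | no |
| no | any | any | no |

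The fourth row is the main route. The fifth should be rare: MCCB comes before the other neuropsychological assessments (Protocol 6.2) and the first dose follows all Visit 2 assessments (Protocol 6.2.2). It exists because the SAP's baseline fallback leaves MCCB out: "If this value is not available, the measurement at the screening visit (Visit 1) will be used, except for MCCB assessments".

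**2. The plan's own figure.** The plan gives no count for this point. Protocol 7.7 gives 200 randomised and 10% dropout, so 200 × (1 − 0.10) = 180 evaluable. That reproduces, but it concerns the primary endpoint and does not say how many patients lack MCCB and still have SCoRS or PANSS.

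**3. Upper bound on the share affected.** Assumptions, not in the documents: MCCB is missed with probability q at each post-baseline visit, the misses at the two visits have correlation φ, and all 200 randomised patients are treated.

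P = q² + φ·q·(1 − q); count = 200·P; SE inflation = 1/√(1 − P) − 1.

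| q | φ | P | Patients of 200 | SE inflation, at most |
|---|---|---|---|---|
| 0.05 | 0 | 0.0025 | 0.5 | 0.13% |
| 0.05 | 0.5 | 0.0025 + 0.5 × 0.0475 = 0.02625 | 5.25 | 1.34% |
| 0.05 | 1 | 0.05 | 10 | 2.60% |
| 0.10 | 0 | 0.01 | 2 | 0.50% |
| 0.10 | 0.5 | 0.01 + 0.5 × 0.09 = 0.055 | 11 | 2.87% |
| 0.10 | 1 | 0.10 | 20 | 5.41% |

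Shares, counts and SE figures are all upper bounds. P counts everyone without a usable post-baseline MCCB. Only those who also have a usable SCoRS or PANSS matter, because a patient missing all three scales adds nothing under either set. The SE column further assumes that each such patient supplies a full Week 12 value.

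A second route agrees. With 180 patients in the FAS and x more, split equally between arms, who have ratings but no MCCB, the FAS standard error is larger by √((180 + x)/180) − 1. That is 1.4%, 2.7% and 5.4% for x = 5, 10 and 20.

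**4. Early discontinuers.** "Study day windows for mapping to analysis visits are presented in Table 6.7: 1". Visit 4 falls at the latest on day 42 + 3 from first dose, which is study day 46. A patient who stops by then and has the eEoT within 7 days (Flow Chart, footnote 2) is rated by day 46 + 7 = 53, or by day 46 + 10 = 56 with the COVID-19 delay in Protocol 10.5. Both lie in the Week 6 window for PANSS (days 2 to 60). For SCoRS, any value from day 2 on maps to Week 12.

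Such a PANSS value informs Week 12 only through the Week 6–Week 12 correlation ρ. With n patients, of whom m = n(1 − P) have Week 12 values, the variance of the Week 12 mean is proportional to (1 − ρ²)/m + ρ²/n when the others are kept, and to 1/m when they are dropped. The SE inflation from dropping them is 1/√(1 − ρ²P) − 1:

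| P | ρ = 0.5 | ρ = 0.7 |
|---|---|---|
| 0.05 | 0.63% | 1.25% |
| 0.10 | 1.27% | 2.54% |

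The values of ρ are assumed. A simulation with 100 per arm and 200,000 runs gave 0.62%, 1.29%, 1.18% and 2.48%, reading across the rows.

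**The case against.** The strongest reply is that nothing here is wrong. Protocol and SAP agree on the set and on its use, and one common efficacy set keeps the same patients across endpoints. The route is also narrow:

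- MCCB is done first at each visit.
- One usable MCCB at either visit keeps the patient in.
- Remote visits are meant to be exceptional.
- Videoconference sub-tests or a delayed final visit can rescue the battery.

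There is no formal testing (Protocol 7.2) and secondary p-values are descriptive (Protocol 7.3.2). The size rests wholly on assumed miss rates. Redacted parts of both documents may hold further sets or sensitivity analyses.

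Most of this stands, and it is why the point is of low severity. It does not remove the point. The rescue routes shrink the group without emptying it. Inference rests on estimated differences, so who enters the estimate still matters. A redacted supplementary analysis would not change the visible primary analysis of these endpoints.

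A reader might infer more than the documents support:

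- That a missed Week 12 MCCB alone excludes a patient. It does not; a usable Visit 4 value is enough.
- That the ratings disappear. They do not: "In subject data listings, all data at scheduled or unscheduled timepoints will be presented". They are absent only from the models.
- That the SCoRS and PANSS results are biased. Any bias depends on why MCCB is missing, and the documents do not allow it to be estimated.
- That all 0.5 to 20 patients would be recovered. These are ceilings.

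**Conclusion.** The concern holds as a cheap improvement of low severity. It is neither an error nor an inconsistency in how the set is defined or used. SCoRS and PANSS are restricted by a scale that their models do not use, and valid ratings can be left out as a result. With assumed MCCB miss rates of 5% to 10% per visit and correlations between visits from 0 to 1, at most 0.25% to 10% of treated patients are affected, with at most 0.1% to 5.4% SE inflation. If those left out are early discontinuers, the ceiling for PANSS at 5% to 10% affected falls to about 0.6% to 2.5%. The true number is unknown and probably small. The primary analysis is not touched.

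**What to change.** In SAP 6.3 and 7.5.2.1, analyse SCoRS and PANSS, each separately, in all Treated Set patients, as randomised, who have a baseline and at least one post-baseline value of that endpoint that SAP 6.7 maps to an analysis visit. Apply the inclusion rules already used for SCoRS and PANSS values of FAS patients. No new on-treatment cut-off is then needed; the readable SAP has none for these scales, since the 11-day residual effect period is defined for safety analysis and the 12-day limit for MCCB only. Keep the MCCB-based FAS for the neurocognitive and overall composites.

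Two departures from the protocol need a line each. The new set differs from Protocol 7.3 and 7.3.2. The screening fallback for baseline in SAP 6.7 already differs from Protocol 7.3, which takes the Visit 2 measurement for all efficacy endpoints. Record the first in the SAP, or align the protocol at the next amendment. For the second, either record it or use the Visit 2 value only.

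The cost is a few sentences and no new data. Patient numbers will differ slightly between endpoint tables, and a few added SCoRS values will come from early-discontinuation visits mapped to Week 12, as the plan already allows for FAS patients.

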## 6.5 POOLING OF CENTRES

This section is not applicable because centre/country is not included in the statistical model.

## 6.6 HANDLING OF MISSING DATA AND OUTLIERS

Unless otherwise specified, missing data will not be imputed and will remain missing. Potential outliers will be reported and analysed as observed.

### MCCB

Handling of missing data in MCCB tests will follow the MCCB Manual (available in the ISF). See [Section 10.1](#) for detailed descriptions and imputation rules.

EoT measurement of MCCB endpoints which were collected >12 days after the last study medication intake date will not be included in the analysis.

### SCoRS

For the 20-item SCoRS assessment, if six or more of the 20 items have missing response, which includes the response of “N/A”, for a subject at a visit, then the SCoRS total score for that subject at that visit is missing. If five or less of the 20 items have missing response, which includes the response of “N/A”, for a subject at a visit, then the item with missing response will be imputed first with the average of the non-missing item values for the subject at the visit, and then SCoRS total score for the subject at the visit will be derived as the sum of the non-missing item values and the imputed item values.

PANSS

PANSS total and subscale scores will be calculated as sums of their constituting item scores. If  $\leq 20\%$  of the items are missing in the calculation of the total or subscale scores, the missing items will be temporarily imputed with the mean of the non-missing item scores. The total or subscale score will then be calculated as the sum of the non-missing and imputed item scores.

For calculation of PANSS total score and the subscale scores, the maximum numbers of missing items allowed are:

PANSS total score:	6 out of 30
Positive Symptom:	1 out of 7
Negative Symptom:	1 out of 7
General Psychopathology:	3 out of 16
Emotional Expression:	0 out of 4
Emotional Experience:	0 out of 3
Marder Negative Factor:	1 out of 7

If more than the maximum allowed number of items are missing, the score will not be calculated.

## 6.7 BASELINE, TIME WINDOWS AND CALCULATED VISITS

In general, baseline value will be the measurement taken on the day of randomization (Visit 2), and prior to the first study medication administration. If this value is not available, the measurement at the screening visit (Visit 1) will be used, except for MCCB assessments.

Baseline for MCCB neurocognitive composite score and related endpoints is defined as the measurements taken at randomization (Visit 2), and prior to the first administration of the study medication.

Analysis visit will be used for by-visit summaries and analysis of efficacy endpoints. Study day windows for mapping to analysis visits are presented in Table 6.7: 1. Actual study day will be calculated starting with day of randomization as Day 1. If more than one assessment is mapped to the same post-baseline analysis visit, the closest assessment to the planned study day will be used. In case of a tie, the earlier assessment will be used.

Table 6.7: 1 Analysis visit windows

Analysis visit	Nominal Timepoint	Planned study day	Actual study day window	
			MCCB*, PANSS	Other efficacy assessments
2	Baseline	1	≤1	≤1
4	Week 6	43	2 – 60	
6/EoT	Week 12	85	≥61	≥2

\*MCCB assessments taken >12 days after the last study medication intake will not be included in the analysis.

Safety endpoints will be summarized based on nominal visits as reported in the CRFs. No re-labelling to analysis visits will be performed.

In subject data listings, all data at scheduled or unscheduled timepoints will be presented.

